3.0 RESEARCH STRATEGY

3.1 Significance

3.1.1. Metatarsophalangeal joint (MTPJ) hyperextension deformity is an important risk factor for skin breakdown in people with diabetes mellitus (DM) having a prevalence as high as 85% in those with DM and a history of ulcers and amputation.² Characteristics of MTPJ deformity are hyperextension of the proximal phalanx on the metatarsal, and prominent metatarsal heads on the bottom of the foot (Fig. 1).^{1, 14} Inter-phalangeal joints may be flexed (claw toe) or flexed and extended (hammer toe).^{14, 15} Our previous work indicated MTPJ angle is the most important structural variable predicting forefoot peak plantar pressure during walking,¹⁶ and multiple clinical studies have linked the deformity to skin breakdown.^{2, 17, 18} 60-70% of the 26 million people with DM in the US have peripheral neuropathy (PN), associated with mild to severe nervous system damage. One in every four patients with DM will develop a foot ulcer^{19, 20} and each treatment of a wound infection is estimated to cost approximately \$28,000 for the 2 years following diagnosis.²¹ Over 80% of the 65,000 diabetes-related amputations performed annually in the US are preceded by a neuropathic ulcer.^{3, 4} The Task Force of the Foot Care Interest Group of the American Diabetes Association indicated the “most common triad of causes that interact and ultimately result in ulceration has been identified as neuropathy, deformity, and trauma.”^{1, 22} Although MTPJ deformity is a common and important acquired neuropathic foot deformity, there is little evidence to guide early detection and treatment to arrest the development and progression of deformity. This study will be the first to examine multiple contributing factors to MTPJ deformity and the potential of a targeted foot specific intervention to de-couple diabetes related mechanisms from MTPJ deformity over 3 years. The results of this study will help identify the primary factors contributing to MTPJ deformity and test an intervention directed at this proposed causal pathway.

3.1.2 Effect of AGEs on lower extremity tissues. Non-enzymatic advanced glycation end-products (AGEs) are protein-sugar complexes that are formed when proteins or lipids are glycated and oxidized after contact with glucose.⁵ AGEs are thought to be irreversibly created and accumulate in tissues, particularly tissues with low protein turnover such as the extra cellular matrix, connective tissue, skin, and tendons.⁵ AGE accumulation increases cross links between the tissues' fibers, making them thicker, stiffer and weaker. The physical properties of the tissue are compromised and are less able to perform their respective function and therefore, more susceptible to injury.^{5, 6, 23} AGEs are primary factors in age-related complications affecting the extracellular matrix and connective tissue and their impact is greatly accelerated in people with DM due to the excess glucose in the blood stream and extracellular matrix.⁵ The accumulation of AGEs may affect essentially every tissue in the neuropathic foot negatively and it is possible that AGEs are the common denominator in the general deterioration of the diabetic foot.⁶ The tissues of particular importance in the development of acquired diabetic foot deformities are the peripheral nerves, muscles, and joints of the lower extremity. (Fig 2)

```

graph TD
    DM[Diabetes mellitus] --> AGEs[Advanced glycation end-products (AGEs)]
    DM --> PNP[Peripheral neuropathy]
    AGEs --> PNP
    AGEs --> LAM[Limited ankle joint mobility]
    AGEs --> IFMD[I intrinsic foot muscle deterioration]
    PNP --> IFMD
    LAM --> IFMD
    IFMD --> MHPM[Metatarsophalangeal hyperextension moment]
    LAM --> MHPM
    MHPM --> MJD[Metatarsophalangeal joint deformity]
    MJD --> EPS[Excessive plantar stress]
    MJD --> NUC[Neuropathic ulceration]
    EPS --> NUC
    NUC --> LEA[Lower extremity amputation]
    
```

Pathway: MTPJ deformity development to lower extremity amputation

Peripheral neuropathy (PN) has long been identified as a primary risk factor for development of neuropathic plantar ulcers because of the distal deterioration of the sensory, motor, and autonomic nerves to the foot.³ AGEs are thought to contribute to the development of PN. Meerwaldt et al (2005)²⁴ and Conway et al (2011)⁷ have used skin autofluorescence (as proposed in this project) to identify significant relationships between estimated AGEs in the skin and symptoms of PN. Meerwaldt et al reported that autofluorescence independently explained 55% of the variance in nerve conduction velocity and amplitude ($r=0.74$, $p<0.01$).

Figure 1. CT image shows MTPJ hyper-extension deformity. Arrows indicate common sites of ulceration.

[figure not shown]

Figure 2. We will investigate the role of metabolic processes (advanced glycation end products), intrinsic foot muscle deterioration, limited joint mobility, and MTPJ hyperextension movement pattern in the presence and progression of MTPJ deformity and the ability to decouple this pathway with a foot specific intervention.

les, and joints of the lower extremity. (Fig 2)

Increased AGEs also contribute to increased stiffness and reduced viscoelasticity of muscle⁸ and tendon²⁵ leading to reduced ability to generate muscle force and sarcopenia. We^{11, 26, 27} and others^{28, 29} have documented the deterioration of lower extremity muscle due to PN, but this proposal will seek to investigate how AGEs may affect muscle through PN and the independent effect from AGEs (see section 3.3.5.).

The link between AGE accumulation, decreased elasticity, increased stiffness, and diabetic limited joint mobility has been established in the upper extremity^{30, 31} and hypothesized for the foot,^{6, 32} but there has been little research directly linking AGEs and musculoskeletal problems of the foot. We¹² and others³³⁻³⁶ have documented the relationship between limited joint mobility in the foot and skin breakdown. In particular, limited ankle dorsiflexion motion has been associated with forefoot ulcers and our randomized controlled trial to surgically increase dorsiflexion motion using an Achilles Tendon Lengthening procedure was effective in reducing the rate of ulcer recurrence during the year following the procedure.³⁷

[name], a co-author on the Conway et al⁷ paper will continue to assist us (see letter of support) in using skin intrinsic fluorescence to estimate the level of skin AGEs. The collagen in skin has low turn-over (15 year),³⁸ so skin autofluorescence is thought to represent the long-term effects of hyperglycemia and oxidative stress.²⁴ We hypothesize that the baseline estimate of AGE level in the skin will be a predictor of baseline, 1.5 year, and 3 year MTPJ alignment (Aim 1 Ho1, Aim 3 Ho4).

3.1.3. Intrinsic foot muscle deterioration. Intrinsic foot muscles insert into the proximal phalanx of the toes and are the only muscles able to flex the MTPJ (Fig. 3, #2).¹⁴ The extrinsic long toe extensor muscle, extensor digitorum longus, has its muscle belly in the leg and the tendons attach to the distal phalanges of the toes, resulting in extension at the MTPJ and interphalangeal joints and dorsiflexion of the ankle (Fig. 3, #1). The distal to proximal peripheral neuropathy associated with diabetes results in intrinsic foot muscle deterioration that precedes extrinsic extensor digitorum longus deterioration (Fig. 3, #3).³⁹⁻⁴¹ The muscle imbalance of weak intrinsic foot muscles in the presence of relatively stronger extrinsic toe extensors, results in a force couple that hyperextends the MTPJ and theoretically contributes to MTPJ deformity.³⁹

We and others have found that people with DMPN indeed have severe deterioration of their intrinsic foot muscles, with a reduction in muscle up to 70%.^{10, 11, 26, 28, 29, 41, 42} (Fig. 4) We have recently developed a reliable (ICC>0.95), valid ($r^2>0.97$, RMSE<5%), and nimble quantitative magnetic resonance imaging (MRI) measure of not only intrinsic foot muscle volume but also fat volume.²⁶ The tool can be used to measure specific slices or can accurately measure the entirety of the intrinsic foot muscle compartment. In our recent publication,¹¹ we compared lean muscle and fat volumes from the talonavicular to the tarsometatarsal joints of participants with DMPN without severe forefoot deformity (n=23) and controls (n=12). The DMPN group had less lean muscle tissue (18.2 ± 11.0 vs. $31.6 \pm 12.8 \text{ cm}^3$, $p<0.01$) and more fat in the intrinsic foot muscle compartment (17.9 ± 10.5 vs. $9.3 \pm 3.8 \text{ cm}^3$, $p<0.01$). Although many others have measured and reported muscle atrophy,^{10, 28, 29, 41, 42} our work and methods are novel in the ability to accurately measure multi-slice volumes of both muscle and fat.

The use of our very precise measurement methods will provide a critical component in the study of the role of muscle atrophy in the development and progression of MTPJ hyperextension deformity. In our work described above, using our quantitative methods in one of the larger reported samples of participants with DMPN, we found a significant correlation between intrinsic foot muscle deterioration and the second MTPJ alignment ($r = -0.51$, $p=0.013$). This correlation increased to $r = -0.81$ ($p<0.01$) when atrophy was severe, marked by intrinsic foot fat volume exceeding muscle volume (n=12). Ledoux et al had similar findings using computed tomography scans. Only study participants with DMPN and deformity had a reduction in intrinsic foot muscle volume compared to those without PN and/or without deformity.⁴³ In contrast, using less precise measurement methods (one slice of the forefoot and smaller sample sizes), Bus et al (2002 and 2009) found no relationship between intrinsic muscle volume and

[figure not shown]

Figure 3. Sagittal MRI slice of DMPN foot with MTPJ hyperextension showing pull from extrinsic long toe extensor tendon (1), diminished pull (2) from atrophied and fat-filled intrinsic foot muscles (3).

[figure not shown]

Figure 4. Coronal MRI through the midfoot of a control (left) and 2 participants with DMPN (center, right). Those with DMPN had decreased muscle volume (dark) and increased fat volume (bright) in the intrinsic foot muscle compartment.

deformity. The ability to measure accurately both muscle and fat, in a large sample of participants with DMPN will assist in clarifying the role of intrinsic foot muscle deterioration in MTPJ deformity development and progression.^{10, 28} Additionally, we believe that intrinsic muscle atrophy alone will not result in MTPJ deformity but must be combined with limited ankle joint mobility and a repetitive MTPJ hyperextension movement pattern for MTPJ deformity to develop and progress.

3.1.4. MTPJ hyperextension movement pattern. A new and innovative aspect of this proposal is that we will test the hypothesis that loss of intrinsic foot muscle volume must be coupled with an MTPJ hyperextension movement pattern to cause MTPJ deformity. (Aim 1 Ho1, Aim 3 Ho4) We operationally **define a MTPJ hyperextension movement pattern as a substantial increase in MTPJ extension with active ankle joint dorsiflexion** (Figs. 3, 10, & 11). Results of this study will help to define the magnitude of a “substantial increase”, but preliminary data in section 3.3.4.4 suggests this value to be 10°. We believe the MTPJ hyperextension movement pattern is the result of increased reliance on the extensor digitorum longus to assist in dorsiflexing the stiff ankle joint during daily activities and a reduction in intrinsic muscle strength to resist MTPJ extension (i.e., sit to stand, Fig. 10).^{13, 44, 45} Repetition of this movement pattern may lead to MTPJ deformity. Supporting that hypothesis, we have found that MTPJ hyperextension deformity was strongly correlated with limited ankle dorsiflexion range of motion ($r=0.69$ to 0.80) in people without DM.¹³ Limited ankle dorsiflexion range of motion is a common impairment in individuals with DMPN,^{12, 36} likely caused by an accumulation of AGES and thickening of the Achilles tendon.²³ We hypothesize, and will test in this proposal, that maximum ankle joint dorsiflexion and MTPJ extension during sit-to/from-stand, will predict MTPJ alignment at baseline, 1.5, and 3 years. (Aim 1 Ho1, Aim 3 Ho4)

3.1.5. Foot Specific Intervention. The relevance and significance of this proposal is enhanced by our integrative study design that includes a foot specific intervention. We hypothesize that the intervention, targeted at the key downstream residuals of diabetes (leg and foot muscle deterioration, limited ankle joint dorsiflexion, and MTPJ hyperextension movement pattern) can decouple disease driven mechanisms from MTPJ hyperextension deformity development and progression. The intervention is a progressive, home based exercise program aimed to increase ankle and foot plantarflexion muscle strength, increase ankle dorsiflexion and toe flexion range of motion, and to retrain individuals to dorsiflex the ankle while keeping the toes in a neutral position (see sec 3.3.5 and appendix A). A trained physical therapist with experience working with older adults with diabetes and foot specific complications will monitor and progress the exercise program assuring participant safety and maximizing exercise benefit.

There has been very little work on the ability of exercise interventions to improve leg and foot muscle strength, ankle dorsiflexion, or foot function in those with diabetes and peripheral neuropathy. In our recent published randomized controlled trial, participants with DMPN performed a progressive walking program that also included select exercises to improve balance, flexibility, and ankle muscle strength. Using this more comprehensive but less focused intervention program, we demonstrated that participants could significantly increase distance walked in 6 minutes and, important for this proposal, ankle dorsiflexion ROM and Foot and Ankle Ability Measure (self-report of foot function) (4.1°, 95% CI = 1.7 to 6.5°; 10.7 points, 95% CI=1.8 to 19.5 points, respectively).^{23, 46} Toe flexion strength gains, up to 36%, have been reported in older people who completed a targeted exercise program⁴⁷ and healthy adults had improved strength and function on high level tasks (vertical jump and 50 meter dash) after completing a toe strengthening program.⁴⁸ We recognize the possibility that neuropathic muscle may have a limited ability to respond to an exercise stimulus. This challenge and the lack of research in this important area make this a proposal that will have exciting and relevant outcomes that will advance our knowledge and understanding of diabetes related complications, their plasticity, and guide treatment decisions.

The **shoulder specific control intervention** is another novel and creative component of our proposal. This control intervention will be useful to participants, will not contaminate the foot specific intervention outcomes, and likely will have stand-alone scientific merit. Our previous and current work investigating shoulder dysfunction in individuals with DM found that 63% of people attending an outpatient Diabetes Center reported shoulder pain or disability and almost all had limited joint mobility that may be a precursor to more severe problems.⁴⁹⁻⁵¹ Shoulder, foot and ankle pathology and may have some of the same contributing factors (i.e., increased AGEs, muscle weakness, decreased movement) in people with DM.^{5, 6, 8, 23, 25, 30, 31} Thus, a shoulder specific intervention will provide an excellent control for the foot specific intervention and meet a need of many of our participants. In addition, the outcome data measured at 6 months, 1.5 and 3 years will provide useful long-term follow-up data that will complement our currently funded, short-term R21 (Grant #: DK100793, Clinical Trials.gov: <https://clinicaltrials.gov/ct2/show/NCT02162212>) to inform patient care and guide future research in the understudied area of upper extremity disabilities associated with DM.

Summary of significance: The cost and burden of care for foot disease in people with DM is staggering. One in four of the 26 million people with DM will develop skin breakdown¹⁹ and the treatment for each wound infection is estimated to cost approximately \$28,000 over the 2 years following diagnosis.²¹ As many as 85% of those with a history of skin breakdown or amputation have forefoot deformity.² This proposal focuses on the significant questions of “what are the causes and predictors of acquired forefoot deformity in people with DMPN and can a foot specific intervention make a difference in the short and long term outcomes?” Previous investigators^{28, 40} have not been able to determine why some people with DMPN develop this deformity and others do not, likely because important factors associated with MTPJ deformity development and progression were not studied. For the first time, we will investigate an innovative and comprehensive set of potentially modifiable causal factors leading to MTPJ deformity, provide an intervention to assess how modifiable the factors are and follow progression over a 3 year time period. A successful foot specific intervention would immediately and easily translate into clinical practice at a very nominal cost to the health care system. For patients with diabetes, a non-invasive intervention that halts or slows the cascade of events leading to amputation would yield improved function and reduced disability. In addition to understanding better the causes of MTPJ deformity, the results of this project will have important implications for understanding other severe and disabling neuropathic foot deformities such as Charcot neuroarthropathy.

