3.3. Approach

3.3.1. Research Design. This research design is illustrated in Fig 5. Aim 1 will use a cross-sectional design to determine baseline relationships between AGE level, intrinsic foot muscle volume, ankle joint mobility, MTPJ movement patterns and MTPJ extension alignment at baseline. Aim 2 is a clinical study with the foot specific intervention focused on improving foot and ankle strength, mobility, and function. The control group will receive a meaningful, comparable, but distinct intervention targeted at improving shoulder mobility, a common limitation in those with DMPN. All participants will repeat testing at 6 months, 1.5 years, and 3 years. Aim 3 will determine the key variables that predict progression of MTPJ extension deformity at 1.5 and 3 years. Intervention status will be entered as a potential predictor variable to examine the ability of a foot specific intervention to impact deformity progression.

Sixty-two participants with DMPN (defined below) and a wide range of MTPJ extension angle will be recruited and followed for 3 years. We will recruit a wide range of MTPJ extension angles to have broad variance in the magnitude and presentation of this deformity so we can understand better the primary factors with which it is associated. We will not break participants into groups based on amount/severity of MTPJ hyperextension allowing us to maintain the continuous nature of important predictors and dependent variables, and hence, increase power of our repeated measures research design.^{55, 56} Only participants with DMPN will

Figure 5: Research Design

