3.3.4.2. Spiral CT Scanning for MTPJ Deformity and Joint Positions: The purposes of using spiral CT scans for this project are to measure: 1) MTPJ alignment over the 3 year follow up period, 2) measure precisely maximum ankle joint dorsiflexion, and 3) maximum MTPJ active flexion in resting position. CT scans and measurements will be taken in 3 positions. At Visit 4 an additional CT scan will be taken of the foot not followed as part of the study for a comparison.

- 1) Resting position - the calf and foot are placed on a positioning device to standardize ankle position in resting position of 30° plantar flexion (approximate mid position of physiological ankle range of motion from 10° dorsiflexion to 50° plantar flexion, see Fig. 7).^{13, 59} The measure of MTPJ angle in resting position will serve as our primary outcome measure defining the amount of MTPJ hyperextension. MTPJ alignment will be defined as the angle between the phalanx and the extension of the bisector of the metatarsal. A larger angle will indicate less deformity.^{13, 67} (Aims 1-3, Fig. 8).
- 2) Maximum active ankle dorsiflexion - The study participant will be instructed to maximally dorsiflex their ankle joint. Maximum active ankle dorsiflexion and concurrent MTPJ angle will provide the measure of ankle mobility for Aims 1 &2 and an indicator of MTPJ hyperextension movement pattern for Aims 1-3. (Fig. 8b)
- 3) Maximum active MTPJ flexion – The study participant will be instructed to maximally flex their MTPJ with their foot supported in the positioning device. Maximum active MTPJ flexion is an exploratory outcome measure that should improve with the foot specific intervention through increasing MTPJ joint mobility and intrinsic muscle strength. (Fig. 8c)

[figure not shown]

Figure 8. CT positions for measuring MTPJ and ankle angles. MTPJ alignment is the angle between the phalanx and the extension of the bisector of the metatarsal. A larger MTPJ angle indicates less deformity.

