Participants will be positioned supine on the CT scanner table using our previously published reliable and precise methods to measure MTPJ angles.^{54, 59, 67-69} Briefly, we use a multi-slice Siemens Sensation 64 CT scanner (Siemens Medical Systems, Inc., Iselin, NJ) that allows a spatial isotropic resolution of 0.6 millimeters (mm) for a clear detailed visualization with a rapid acquisition time (gantry rotation speed of 0.5 seconds). The following CT parameters will be used to acquire the scans: 0.5 second rotation time, 64×0.6 mm collimation, 220 mAs, 120 kVp, a pitch of one, and a 512×512 matrix. The lower one third of the leg and the entire foot are scanned. Acquisition time will depend slightly on the size of the subject's foot but generally is less than 2 minutes of x-ray tube time for all 3 scanning positions. The CT projection data sets will be reconstructed with a resolution of approximately $0.6 \times 0.6 \times 0.6$ mm³. The CT data will be de-identified, archived on DVDs using DICOM format, and processed in the Electronic Radiology Laboratory. The SCT data will be converted from DICOM format to an Analyze software file format⁵⁴ (ANALYZE Software, Biomedical Resource Mayo Clinic, Rochester, MN). As illustrated in Figure 8, the following angles will be measured for all three scans: (1) MTPJ angle: 180° minus the angle between the phalanx and metatarsal for all five metatarsals and (2) Ankle joint position: tibia and a line drawn between the bottom of the calcaneus and the second metatarsal head.⁵⁴

Preliminary Data: We recruited 19 participants with DMPN (mean age 59 ± 9 years) who met the identical inclusion and exclusion criteria proposed in this project. MTPJ alignment in resting will be reported in combination with the intrinsic muscle volumes in section 3.3.4.3, Fig 9. During the maximum active ankle joint dorsiflexion task, MTPJ angle was negatively correlated with maximum ankle joint dorsiflexion (Spearman's rho $r = -.58$, $p < .01$). This finding supports the hypothesis that the MTPJ deformity is

associated with limited ankle joint mobility. This proposal will examine the role of limited ankle joint mobility in MTPJ deformity development and progression and the ability of a foot specific intervention to improve ankle dorsiflexion range of motion.

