This study uses fifty 10 mm, reflective markers to define 5 segments on each leg: shank, hindfoot, forefoot, second metatarsal, and second toe proximal phalanx. Bilateral kinematic data will be collected using an 8 camera 3D motion capture system (Vicon, Los Angeles, CA, USA) and methods from [name] recent publications.^{52, 53} All data will be processed and analyzed using Vicon Nexus, Visual3D (C-motion, Inc., Rockville, MD), and MatLab (Mathworks, Natick, MA) software, using established and published methods.⁵² The participants will perform the following tasks:

- 1) **Sit-to/from-stand task:** 3 trials of coming from sit-to-stand and stand-to-sit. This is a weight-bearing task requiring recruitment of the ankle dorsiflexors to control the tibia. We hypothesize MTPJ excursion from sit-to/from-stand will predict MTPJ alignment at baseline, 1.5, and 3 years (Aims 1 & 3) and MTPJ excursion will be reduced after the foot specific intervention (Aim 2).

- 2) **Ankle Dorsiflexion/Plantarflexion Task:** 5 trials of seated full ankle dorsiflexion and plantarflexion with the knee in full extension. We predict dorsiflexion will be decreased and MTPJ excursion increased in those with MTPJ deformity (Aim 1) and that dorsiflexion will increase and MTPJ excursion will decrease after the foot specific intervention (Aim 2).
- 3) **Unilateral heel rise task:** 10 trials of unilateral heel rise (both right and left). The unilateral heel rise task provides an indicator of foot function, especially intrinsic muscle force production to plantarflex the forefoot on the hindfoot while lifting 100% of body weight. We hypothesize that the amount of forefoot relative to hindfoot plantarflexion during heel rise will be associated with intrinsic muscle volume and improve with the foot specific intervention.
- 4) **Walking task:** 5 trials of self-selected pace will be collected on a small subset of individuals. Participants may agree to participate in additional walking trials at various speeds and time.

Preliminary Data. Our study team, led by [name], developed and published work investigating the intersegmental foot motions of people with DMPN and medial column deformity and those that received a tendon transfer surgery to correct foot drop.^{52, 53} We will be using the same intersegmental foot model for this project and have added segments for the second metatarsal and proximal phalanx of the second toe to capture 2nd MTPJ motion during our selected tasks.

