Aim 1: A multiple linear regression analysis will be used to test Aim 1. The primary dependent variable for Aim 1 will be baseline MTPJ alignment. The independent variables (predictors) for Aim 1 will be AGE level, intrinsic foot muscle volume, maximum ankle dorsiflexion, and MTPJ extension excursion during sit to stand. A Pearson correlation matrix will be obtained on all variables to understand better inter correlations. Adjusted R square from the multiple linear regression model will be obtained.

Aim 2: A repeated measures ANOVA analysis will be used to estimate the effect of the intervention by determining the between group changes over time in the primary outcome measures MTPJ extension alignment and the secondary outcome measures of intrinsic muscle volume, ankle joint dorsiflexion range of motion, MTPJ extension excursion during sit-to/from-stand and Foot and Ankle Ability Measure. Contrasts will be used to determine mean differences of interest.

Aim 3 Ho3: MTPJ deformity progression will be calculated as progression every 1.5 years (MTPJ deformity at baseline – MTPJ deformity at 1.5 years and MTPJ deformity at 1.5 years – MTPJ deformity at 3 years). Means and standard deviations for these differences will be obtained and paired t-tests will be performed to test for significant progression every 1.5 years. The proportion of individuals with DMPN and MTPJ deformity progression at 4 degrees or more within 1.5 years will be calculated with 95% confidence interval.

Aim 3 Ho4: MTPJ deformity progression will be assessed as progression at 1.5 and 3 years (MTPJ deformity at baseline – MTPJ deformity at 1.5 years and MTPJ deformity at baseline – MTPJ deformity at 3 years). Analysis of covariance model will be fitted to these two progression variables with intervention status as the major predictor adjusting for baseline measures of AGE level, intrinsic foot muscle volume, MTPJ extension excursion during sit to stand.

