All statistical tests will be two-sided with a significance level of 0.05 and performed with SAS 9.4. Careful attention will be paid to ensuring that data satisfy assumptions required of a particular analytic strategy. Thus, paired t-tests will only be accepted as valid if normality assumptions are satisfied. Similarly, we will evaluate regression residuals before we reach conclusions based on linear regression analysis. When required assumptions are violated, we will explore the use of data transformations and potentially, perform some analyses using non-parametric or semi-parametric methods based on the rank of some variables. In the event of multicollinearity with numerous predictors in regression models, highly redundant variables will be eliminated from the analyses, or where possible, composite variables will be formed to capitalize on the higher reliability of combined measures. Sample size limitations and potential multicollinearity may preclude the examination of all predictors in one analysis. To avoid this problem, we will examine the impact of predictors individually or in small, conceptually sensible, subsets.

3.3.7. Proposed Timeline and Plans for Future Studies.

We propose to complete the aims of this project in 5 years with the following milestones:

9/1/2015 – start date; Year 1: Methods and personnel are ready to begin testing immediately. Based on current recruitment methods, we are confident we can recruit and test 4 subjects per month. Therefore, we plan to conduct all baseline testing in the first 16 months of the study; 48 in year 1 and 14 in year 2. Data processing and entry into databases will occur on an on-going basis. Intervention will be initiated immediately after baseline testing has been completed

Year 2: Participant recruitment, baseline testing, intervention and 6 month follow up testing will be completed in year 2. Data analysis for baseline measures and the manuscript related to Aim 1 will be completed by the end of year 2. 1.5 year re-testing will begin on 24 subjects. Data analysis for Aim 2, 6 month data will be analyzed and the related manuscript prepared for publication.

Year 3: Complete 1.5 year re-testing on remaining 38 participants for total of 62 participants. Analyze and summarize all data.

Year 4: Complete 3 year retesting on 48 participants.

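### Ankle dorsiflexion is promised as a predictor at 1.5 and 3 years under Aim 3 Ho4, but no planned Aim 3 analysis includes it

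*Combined protocol and SAP*

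**What the plan says.** Section 3.1.4 commits the study to testing that "maximum ankle joint dorsiflexion and MTPJ extension during sit-to/from-stand, will predict MTPJ alignment at baseline, 1.5, and 3 years", tagged to Aim 1 Ho1 and Aim 3 Ho4. Section 3.3.4.2 (preliminary data) adds: "This proposal will examine the role of limited ankle joint mobility in MTPJ deformity development and progression". Section 3.3.1 describes the purpose of the third aim: "Aim 3 will determine the key variables that predict progression of MTPJ extension deformity at 1.5 and 3 years".

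The analysis section, 3.3.6, treats the two aims differently:

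- **Aim 1 (baseline).** The predictors "for Aim 1 will be AGE level, intrinsic foot muscle volume, maximum ankle dorsiflexion, and MTPJ extension excursion during sit to stand". Dorsiflexion is one of four.
- **Aim 3 Ho4 (1.5 and 3 years).** An ANCOVA on change from baseline, with intervention status as the main predictor, "adjusting for baseline measures of AGE level, intrinsic foot muscle volume, MTPJ extension excursion during sit to stand". Dorsiflexion is not listed.
- **Aim 3 Ho3.** Paired t-tests and a proportion, with no predictors.

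The measurement sections side with the Ho4 model. Section 3.3.4.2 says the active-dorsiflexion CT scan "will provide the measure of ankle mobility for Aims 1 &2 and an indicator of MTPJ hyperextension movement pattern for Aims 1-3", so as a measure of ankle mobility it is not assigned to Aim 3. Section 3.3.4.4 ties the dorsiflexion task to Aims 1 and 2, and ties sit-to-stand excursion to Aims 1 and 3 as well as Aim 2.

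**The concern.** A hypothesis that the plan says it will test has no analysis attached to it. Ho4 is the only model of predictors of progression. Of the variables that sections 3.1.2 to 3.1.4 tag to Ho4, dorsiflexion alone is missing from it. No reason is given, and Aim 1 fits dorsiflexion beside the same three covariates.

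Limited ankle mobility is also a named target of the intervention (section 3.1.5). A reader of the results will therefore expect to learn whether baseline dorsiflexion is associated with progression. Without a prespecified model, the question either goes unanswered or is answered by a model chosen after the data are seen.

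**Working it through.** **1. Side-by-side comparison**

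| Predictor | Tagged to Ho4 in section 3.1 | In Aim 1 regression | In Ho4 ANCOVA |
|---|---|---|---|
| AGE level | yes (3.1.2) | yes | yes |
| Intrinsic muscle volume | yes (3.1.4) | yes | yes |
| Sit-to-stand MTPJ excursion | yes (3.1.4) | yes | yes |
| Maximum ankle dorsiflexion | yes (3.1.4) | yes | **no** |

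The outcome also differs. Section 3.1.4 speaks of alignment at each time point, whereas Ho4 models change from baseline.

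The plan gives no power or precision figure for Ho4, so there is none to reproduce.

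**2. Is degrees of freedom a reason to leave it out?**

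Completers: 62 × (1 − 0.20) = 49.6, about 50. The planned model has intervention plus three covariates, so residual df = 50 − 5 = 45. A fourth covariate gives 44. If it explains nothing, the 95% CI for the intervention effect widens by the factor [t(0.975, 44)/t(0.975, 45)] × √(45/44) = 1.012, about 1.2%. Replacing excursion with dorsiflexion leaves df at 45. Loss of df does not explain the omission.

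**3. Which model would answer the question?**

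This depends on the pathway. In the diagram in section 3.1.2, limited ankle mobility reaches deformity only through muscle deterioration and the hyperextension moment. Section 3.1.4 describes the movement pattern as a consequence of the stiff ankle. Excursion may therefore lie between dorsiflexion and progression.

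Assumptions: n = 50, two-sided 0.05, dorsiflexion–excursion correlation 0.58, and progression driven by excursion alone with R² 0.10 or 0.16. The 0.58 is the size of the pilot correlation in section 3.3.4.2 between CT MTPJ angle and dorsiflexion, which is a different pair of variables. The 0.16 is the square of the baseline pilot r = 0.40 in section 3.3.4.4 and is not a progression estimate.

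- R² carried by dorsiflexion when excursion is left out: 0.58² × 0.10 = 0.034; 0.58² × 0.16 = 0.054.
- R² unique to excursion when both are in: (1 − 0.58²) × 0.10 = 0.066; (1 − 0.58²) × 0.16 = 0.106.
- Variance inflation factor: 1/(1 − 0.58²) = 1.51.

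| Simulated share with p < 0.05 | R² 0.10 | R² 0.16 |
|---|---|---|
| Dorsiflexion, excursion left out | 24% | 36% |
| Dorsiflexion, both in the model | about 5% | about 5% |
| Excursion, dorsiflexion left out | 60% | 81% |
| Excursion, both in the model | 43% | 63% |

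On this pathway, a joint model alone would show nothing for dorsiflexion and would cost power for excursion.

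**4. The opposite assumption**

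Suppose dorsiflexion is the only true predictor, with R² 0.05, 0.10 or 0.16. Excursion, with dorsiflexion left out, is then significant in about 14%, 24% and 35% of trials at correlation 0.58, and about 7%, 10% and 13% at 0.3. It returns to about 5% with dorsiflexion in the model. At zero correlation there is no distortion.

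**5. What the joint model could detect**

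Noncentral F with 1 and 44 df, noncentrality = n·ΔR²/(1 − R² of the full model), other terms assumed to explain 10% to 37%. Power for dorsiflexion is 39–53% at an added R² of 0.05, 69–85% at 0.10 and 90–98% at 0.16. A null result would not exclude a small role.

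**The case against.** **The tag may simply be loose.** Sections 3.3.4.2, 3.3.4.4 and 3.3.6 are the operational text, and they agree in keeping ankle mobility out of Aim 3. The statements to the contrary are in the background section and in a closing line on pilot data. This is a fair reading, and it is why limiting the claim to baseline is an acceptable repair. It does not remove the disagreement. The formal wording of Ho4 was not in the text available to me, so the point rests on the tags in section 3.1.4.

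**Section 3.3.6 already allows a separate look.** It says the team may "examine the impact of predictors individually or in small, conceptually sensible, subsets". That would permit a dorsiflexion model. However, it is a contingency for sample-size or collinearity limits and names no predictor, so it does not prespecify one.

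**A reader might infer that the Ho4 model will wrongly credit excursion with dorsiflexion's effect.** The documents do not support that as a finding. It needs a direct effect of dorsiflexion and a correlation that the plan does not report, and the plan's own diagram points the other way.

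**A reader might also infer that the treatment comparison is biased.** It is not. Allocation is randomised, and leaving out a baseline covariate does not bias the comparison.

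**Aim 3 is declared exploratory.** This is true, and it limits the weight of the point. It does not supply the missing analysis.

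**Conclusion.** The inconsistency is real. The dorsiflexion part of Ho4 has no planned estimate at 1.5 or 3 years. The loss is one unanswered exploratory hypothesis and a predictor model that is harder to interpret. The Aim 1 test at baseline and the randomised comparison stand. The point merits correction before analysis but does not threaten the trial's main conclusions.

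The textual conflict is certain on the available text. Whether the omission was intended is not known. All power and misattribution figures rest on assumed R² values and correlations, and they show only that the choice between a separate and a joint model matters.

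**What to change.** Keep the planned Ho4 ANCOVA unchanged and add to section 3.3.6, as prespecified exploratory analyses at 1.5 and 3 years:

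1. A model with intervention status, AGE level, muscle volume and baseline CT maximum ankle dorsiflexion, without excursion. This estimates the total association.
2. The same model with excursion added. This estimates the association not passing through excursion.

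Report each coefficient with its 95% CI, and state that a null joint coefficient does not rule out an effect through excursion. Add Aim 3 to the dorsiflexion tags in sections 3.3.4.2 and 3.3.4.4. State that the Ho4 outcome is change from baseline, so that section 3.1.4 matches section 3.3.6.

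If dorsiflexion was left out on purpose, restrict the claims in sections 3.1.4 and 3.3.4.2 to baseline instead.

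Cost: no new data, since the CT measure is already taken at baseline. There are two extra exploratory fits at each of two time points (2 × 2 = 4), with more coefficients to interpret cautiously. The joint version has lower power for excursion, which is why it should accompany the planned model and not replace it.
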